10.2 DETERMINATION OF SAMPLE SIZE

This study is designed to demonstrate the non-inferiority of different intervals of administration of nOPV2 (1-week and 2-week intervals) *versus* the standard 4-week interval based on the seroconversion rates of type 2 polio neutralizing antibodies 28 days following the second nOPV2 administration. Non-inferiority would be verified if the lower bound of the two-sided 95% CI around each difference (shorter interval minus standard interval) is greater than -10%.

The nOPV2 vaccine has recently been demonstrated to be non-inferior to Sabin-strain mOPV2 in a Phase 2 study⁸. In this Phase 2 study, among infants aged 18 weeks who had previously been vaccinated with bOPV and IPV, and using a 4-week interval between 2 doses, the cumulative seroconversion rates were near 100%, similar to the mOPV2 historical control group. A prior study of dosing intervals of 1, 2, and 4 weeks conducted

14 August 2021 (Version 1.0)

with mOPV2 in Bangladesh demonstrated seroresponse rates of 93.1%, 95.5% and 97.2% respectively, with lower confidence bounds of 88.3%, 91.3%, and 93.7%¹⁷.

This study will be conducted in the Dominican Republic, and it is not anticipated that immune response rates will be lower than those observed in the previous mOPV2 study. Therefore, with a conservative assumed cumulative 2-dose seroconversion rate of 85% in each group, 270 evaluable subjects per group are required to demonstrate non-inferiority of each of the shorter intervals to the standard interval, using margin 10%, two-sided Type I error rate of 5%, and requiring 90% power. This will be further increased to 300 per group to account for loss to follow-up or other loss from the evaluable population.

11. ADVERSE EVENT REPORTING

11.1 DEFINITIONS

11.1.1 Adverse Events

An AEFI has been defined by the working group on vaccine pharmacovigilance of the Council for International Organizations of Medical Sciences and the WHO as “any untoward medical occurrence which follows immunization and which does not necessarily have a causal relationship with the usage of the vaccine. The AE may be any unfavorable or unintended sign, abnormal laboratory finding, symptom or disease”

An AEFI can therefore be any unfavorable and unintended sign (including an abnormal laboratory finding), symptom, or disease (new or exacerbated) temporally associated with the use of a vaccine product.

Examples of an AE include:

- Exacerbation of a chronic or intermittent pre-existing condition including either an increase in frequency and/or intensity of the condition.
- New conditions detected or diagnosed after vaccine administration even though they may have been present prior to the start of the study.
- Signs, symptoms, or the clinical sequelae of a suspected interaction.
- Signs, symptoms, or the clinical sequelae of a suspected overdose of either vaccine or a concurrent medication (overdose per se should not be reported as an AE/SAE).
- Signs, symptoms temporally associated with vaccine administration.
- Pre- or post-treatment events that occur as a result of protocol-mandated procedures (i.e. invasive procedures, modification of subject's previous therapeutic regimen).

Solicited AEs are described in Section 11.1.2. All other AEs occurring between 8 and 28 days after each vaccination will be recorded as unsolicited AEs.

Examples of an AE DO NOT include:

- Medical or surgical procedures (e.g. endoscopy, appendectomy); the condition that leads to the procedure is an AE/SAE.
- Situations where an untoward medical occurrence did not occur (e.g. social and/or convenience admission to a hospital, admission for routine examination).
- Anticipated day-to-day fluctuations of pre-existing disease(s) or condition(s) present or detected at the start of the study that do not worsen.
- Pre-existing conditions or signs and/or symptoms present in a subject prior to the study vaccination. These events will be recorded in the medical history section of the eCRF.

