This study will be conducted in the Dominican Republic, and it is not anticipated that immune response rates will be lower than those observed in the previous mOPV2 study. Therefore, with a conservative assumed cumulative 2-dose seroconversion rate of 85% in each group, 270 evaluable subjects per group are required to demonstrate non-inferiority of each of the shorter intervals to the standard interval, using margin 10%, two-sided Type I error rate of 5%, and requiring 90% power. This will be further increased to 300 per group to account for loss to follow-up or other loss from the evaluable population.

Immunogenicity

At each pre-and post-vaccination time point where neutralizing antibody titers are obtained:

- Cumulative seroconversion rates (with 95% exact CIs) will be computed from Day 0 at post-vaccination time points. Seroconversion is defined as seropositive (reciprocal titer ≥ 8) in those initially seronegative, or among those initially seropositive, as a minimum 4-fold higher titer (and seropositivity) than that which is expected due to maternal antibodies, using an exponential model to estimate the maternally-derived antibody titers at post-vaccination time points from the pre-vaccination time point, assuming a half-life of 28 days.
- Seroprotection rates (with 95% exact CIs) will be computed
- Geometric mean and median neutralizing antibody titers (with 95% CIs) will be computed
- Plots of the reverse cumulative distribution of antibody titers will be generated for each group.
- Geometric mean fold-rise (with 95% exact CIs) will be computed

Safety

Safety parameters will be tabulated and analyzed descriptively.

Analyses described below will be performed for solicited and unsolicited AEs by severity as well as for SAEs and IMEs. Events will only be considered as solicited AEs if onset occurs within 7 days of a vaccine administration. All events with onset between Days 8 and 28 post-vaccination will be considered unsolicited AEs, with only SAEs and IMEs recorded after 28 days post-last-vaccination.

The original terms used in the designated sections of the electronic case report forms by Investigators to identify unsolicited AEs will be fully described and coded according to the Medical Dictionary for Regulatory Activities.

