3.2 SECONDARY ENDPOINTS

Immunogenicity:

- Geometric mean and median titers of type 2 polio neutralizing antibodies Day 0 and 28 days after the second dose of nOPV2 when administered 1, 2, or 4 weeks apart.
- Cumulative fold-rise (from Day 0) in titers of type 2 polio neutralizing antibodies 28 days after the second dose of nOPV2 when administered 1, 2, or 4 weeks apart. Cumulative fold-rise will be computed relative to the expected level of maternally-derived antibody titers in accordance with the seroconversion definition.
- Fold-rise (from post-dose-1 level) in titers of type 2 polio neutralizing antibodies 28 days after the second dose of nOPV2 when administered 1, 2, or 4 weeks after dose-1. This fold-rise will be computed from the level attained following the first dose, with the pre-dose-2 serum sample.
- Seroprotection rate to poliovirus type 2, at Day 0 and 28 days after the second dose of nOPV2 when administered 1, 2, or 4 weeks apart.
Seroprotection rate is defined as the percentage of subjects with type 2-specific antibody titers $\geq 1:8$.
- Geometric mean and median titers of type 2 polio neutralizing antibodies 1, 2, and 4 weeks after 1 dose of nOPV2.
- Fold-rise in titers of type 2 polio neutralizing antibodies 1, 2, and 4 weeks after 1 dose of nOPV2. This fold-rise will be computed relative to the expected level of maternally-derived antibody titers in accordance with the seroconversion definition.
- Seroconversion rate 1, 2, and 4 weeks after 1 dose of nOPV2.
- Seroprotection rate 1, 2, and 4 weeks after 1 dose of nOPV2.

Safety:

- Incidence of SAEs and IMEs as of the informed consent signature date and throughout the study period in all groups by severity and causal association.
- Incidence of mild, moderate and severe solicited AEs (fever, vomiting, abnormal crying, drowsiness, loss of appetite, diarrhea and irritability) for 7 days after each dose of study vaccine in all groups.
- Incidence of mild, moderate and severe unsolicited AEs for 28 days after each dose of study vaccine by causal association in all groups.

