10.1.5 Safety Data

For an overview safety endpoints, see Section 3.

Safety parameters will generally be tabulated and analyzed descriptively, in the TVP, according to the actual administration interval received. Solicited events will be summarized in the Reactogenicity Population, according to the actual administration interval received. Additional analyses will aggregate across all groups following each dose and overall, including solicited events following each dose independently and overall (TVP, all groups combined), unsolicited events at any time point (TVP, all groups); the SAP will provide further detail.

Analyses described below will be performed for solicited and unsolicited AEs by severity, as well as for SAEs and IMEs. Events will only be considered as solicited if onset occurs within 7 days of a vaccination. All events with onset between Days 8 and 28 post-vaccination will be considered unsolicited. Any SAEs and IMEs will be collected from the date of the informed consent signature throughout the study and will be analyzed with unsolicited events, as well as separately.

The original terms used in the designated sections of the eCRFs by Investigators to identify AEs will be fully described and coded according to the MedDRA.

All AEs will be summarized by group, type, by post-vaccination timepoint and overall (regardless of timing of onset), by severity and occurrence in relation to vaccination, and overall, separately for solicited and unsolicited AEs. Determination of causal association to the study vaccine will be assigned using the individual causality assessment algorithm published by WHO in 2013¹⁸. All SAEs, IMEs and unsolicited AEs will be deemed eligible for causality assessment by the investigator or the safety monitor. After applying the Adverse Event Following Immunization (AEFI) causality algorithm, the SAE, IME or unsolicited AE will be classified as consistent or inconsistent with causal association to immunization; those which meet the definition of causality will be defined as reactions (respectively, serious adverse reactions [SARs], important medical reactions and unsolicited adverse reactions). Events with insufficient or conflicting evidence to make a determination of association will be deemed indeterminate according to the algorithm.

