11.1.2 Solicited Adverse Events

A solicited AE is one that is prelisted in the electronic diary card (paper diary card could be used as back up).

In this study, fever, vomiting, crying abnormal, drowsiness, loss of appetite, diarrhea and irritability will be solicited for 7 days after each study vaccine administration.

Subjects' parent(s) and/or guardian(s) will be provided with an electronic diary. A paper diary card will be provided as back up. This will include the definitions of mild, moderate and severe AEs, as described in Table 4, to facilitate the assessments of the level of functional impairment for each experienced AE. Any solicited AEs reported in the diary will be reviewed by the Investigator during the phone calls or on-site visits that will be scheduled 7 days after each dose of study vaccine.

Axillary temperature should be measured in the evening using the thermometer provided. Should additional temperature measurements be performed at other times of day, the highest temperature must be recorded in the electronic diary.

11.1.3 *Serious Adverse Events*

The Investigator will be responsible for recording and reporting within 24 hours and according to regulatory timelines all SAEs observed during the study (treatment and follow-up) period.

An SAE, experience or reaction, is any untoward medical occurrence (whether considered to be related to study drug or not) that at any dose:

- Results in death.
- Is life-threatening (the subject is at a risk of death at the time of the event; it does not refer to an event which hypothetically might have caused death if it were more severe).
- Requires inpatient hospitalization or prolongation of existing hospitalization: Hospital admissions and/or surgical operations planned before or during a study are not considered AEs if the illness or disease existed before the subject was enrolled in the study, provided that it did not deteriorate in an unexpected way during the study.
- Results in persistent or significant disability/incapacity.
- Is a congenital abnormality/birth defect detected only after study inclusion.

11.1.4 *Important Medical Event*

The Investigator will be responsible for recording and reporting within 24 hours and according to regulatory timelines all IMEs observed during the study (treatment and follow-up) period.

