11.3 CAUSALITY ASSESSMENT

The investigator is obligated to assess the relationship between investigational vaccine and the occurrence of each unsolicited AE/SAE/IME. The investigator will use clinical judgement to determine the relationship. Alternative plausible causes, such as natural history of the underlying diseases, concomitant therapy, other risk factors, and the temporal relationship of the event to the investigational vaccine will be considered and investigated. The investigator will also consult the Investigator's Brochure to determine his/her assessment.

Causality should be assessed by the investigator using AEFI causality algorithm developed by WHO for individual AEFI evaluation¹⁸. When appropriate information is available the investigator should arrive to the following possible conclusions:

Figure 1. Adverse Event Following Immunization Causality Algorithm

*B1 : Potential signal and maybe considered for investigation

SAEs considered to be causally related to the vaccination will be termed SARs.

If an event meets the criteria to be determined as ‘serious’ (see Section 11.1.3), additional examinations/tests will be performed by the investigator in order to determine ALL possible contributing factors for each SAE.

Possible contributing factors include:

- Medical history.
- Other medication.
- Protocol required procedure.
- Other procedure not required by the protocol.
- Lack of efficacy of the vaccine, if applicable.
- Erroneous administration.
- Other cause (specify).

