11.6 RECORDING OF ADVERSE EVENTS

All AEs occurring within 28 days of each vaccination and all SAEs occurring during the clinical investigation must be documented in the source documents and on the AE forms of the eCRF. The Investigator will inquire about the occurrence of AEs/SAEs at every visit/contact during the study.

Whenever possible, diagnoses should be given when signs and symptoms are due to a common etiology (e.g., cough, runny nose, sneezing, sore throat, and head congestion should be reported as “upper respiratory infection”). Investigators must record their opinion concerning the relationship of the (S)AE to the study vaccine in the source documents and on the eCRF. All measures required for (S)AE management must be recorded in the source documents and reported according to Sponsor’s instructions.

All AEs occurring at any time during the study will be followed by the Investigator until satisfactory resolution (e.g., value back to baseline value) or stabilization or until final database lock. If necessary, in order to obtain additional information to ensure safety to the subject, additional blood and urine samples may be taken at the discretion of the Investigator. Certain long-term AEs related to therapy cannot be followed until resolution within the setting of this study. In these cases follow-up will be the responsibility of the treating physician.

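### As worded, the unsolicited-AE rule starts at Day 8, so an unlisted, non-serious AE in the first week after dose 1 (and on Days 29-35 in Group C) has no class, contrary to the 28-day safety endpoint.

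*Combined protocol and SAP*

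**What the plan says.** **Classification rules.** Section 11.1.2 defines the solicited class by a list: "A solicited AE is one that is prelisted in the electronic diary card". The seven terms are fever, vomiting, abnormal crying, drowsiness, loss of appetite, diarrhea and irritability, and they "will be solicited for 7 days after each study vaccine administration". Section 11.1.1, immediately after pointing to that list, deals with the rest: "All other AEs occurring between 8 and 28 days after each vaccination will be recorded as unsolicited AEs". Section 10.1.5 gives the analysis rule: "All events with onset between Days 8 and 28 post-vaccination will be considered unsolicited". The safety paragraph of the synopsis repeats it: "All events with onset between Days 8 and 28 post-vaccination will be considered unsolicited AEs".

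**Endpoint, collection and recording.** These run over the full 28 days with no Day 8 start. The secondary endpoint in Section 3.2 is "Incidence of mild, moderate and severe unsolicited AEs for 28 days after each dose of study vaccine by causal association in all groups". Sections 8.1 and 8.3 and footnote g of each schedule table collect unsolicited AEs for 28 days after each dose. The closing part of Section 10.1.5 summarizes unsolicited AEs within 28 days of any dose. Section 11.6 states: "All AEs occurring within 28 days of each vaccination and all SAEs occurring during the clinical investigation must be documented".

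**Causality.** Section 11.3 requires the investigator to assess the relationship of the vaccine to "the occurrence of each unsolicited AE/SAE/IME". Section 10.1.5 names the same three classes as eligible for the WHO algorithm.

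**The concern.** The two classes do not meet. Take a rash on Day 3 after dose 1, not serious and not an IME, as an illustration. It is not on the diary list, so it is not solicited. It starts before Day 8, so Section 11.1.1 does not make it unsolicited. Section 10.1.5 tabulates AEs separately for solicited and unsolicited events and provides no third table. A programmer who applies the stated rule would have nowhere to put the event, and the causality classification in Sections 10.1.5 and 11.3 would not clearly reach it.

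At stake is a named secondary endpoint, unsolicited AEs over 28 days after each dose by causal association, in a trial whose safety objective is framed by dosing interval. Because the gap is set by the dose days, it is not the same size in the three groups.

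**Working it through.** The plan states no figure here to reproduce. The check has two parts: set the rules side by side, then count the days that the literal rule leaves uncovered.

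**1. Rules for an unlisted, non-serious, non-IME event on Day 3 after dose 1**

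| Place | Rule | Result |
|---|---|---|
| 11.1.2 | Solicited only if on the diary list | Not solicited |
| 11.1.1 | Other AEs unsolicited on Days 8-28 | Not unsolicited |
| 10.1.5, synopsis | Events on Days 8-28 are unsolicited | Silent |
| 3.2, 8.1, 8.3, schedule footnotes | Unsolicited AEs over 28 days | Within the window |
| 11.6 | All AEs within 28 days are recorded | Recorded |

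The last two rows show that such an event is meant to be captured. They conflict with the classification rule and do not supply the missing class.

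**2. Days covered by no Day 8-28 window**

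Inputs: dose days from Section 4.1 (A: 0 and 7; B: 0 and 14; C: 0 and 28). With dose 2 on day d, the period runs from Day 0 to Day d + 28, which is d + 29 days. Covered days are the union of 8 to 28 and d + 8 to d + 28.

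| Group | Dose 1 window | Dose 2 window | Uncovered days | Share of days |
|---|---|---|---|---|
| A | 8-28 | 15-35 | 0-7 | 8/36 = 22.2% |
| B | 8-28 | 22-42 | 0-7 | 8/43 = 18.6% |
| C | 8-28 | 36-56 | 0-7 and 29-35 | 8 + 7 = 15; 15/57 = 26.3% |

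**The week after dose 2.** In Group B (Days 14-21) all of it lies inside dose 1's Day 8-28 window. In Group A (Days 7-14) all of it does except Day 7 itself. In Group C (Days 28-35) only Day 28 does.

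**Sensitivity.** Tables 1 to 3 allow dose 2 up to 2 days late. With dose 2 on Day 9, 16 or 30, the uncovered days are 8 of 38 (A), 8 of 45 (B) and 17 of 59 (C).

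**Days 0-28 after each dose instead.** No day is uncovered in any group at the nominal schedule. If dose 2 in Group C falls on Day 30, Day 29 alone is outside both windows.

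**3. Overlap**

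The windows also classify some events twice. A fever on Day 9 in Group A is 2 days after dose 2, hence solicited, and 9 days after dose 1, hence unsolicited under Section 10.1.5.

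**The case against.** A reader might infer that first-week events are lost, or that the safety objective would be answered without the first week. The documents do not support that. Section 11.6 puts every AE within 28 days of a dose into the source documents and the eCRF, and requires the investigator's opinion on relationship. The schedules mark an unsolicited-AE check at the Day 0 and Day 7 contacts, which would serve little purpose under a true Day 8 start. Diary terms are captured in the first week, and SAEs and IMEs from consent onward. Nor does the gap follow every dose: after dose 2 it is essentially confined to Group C.

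The sentence in Section 10.1.5 and the synopsis also has a milder reading. It follows directly on the rule that an event is solicited only with onset within 7 days, so it may be meant to move late-onset diary terms into the unsolicited class. It does not say that only Day 8-28 events are unsolicited. Section 10.1.5 further says that all AEs are summarized regardless of timing of onset. Safety is secondary and descriptive, and Section 10.1 leaves detail to a SAP to be finalized before database lock.

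All of this stands against any claim of lost data. It does not remove the contradiction. The milder reading does not fit Section 11.1.1, which concerns AEs other than the solicited ones and is worded as a recording rule. The sentence about summarizing all AEs itself splits them into solicited and unsolicited. Section 11.6 secures entry in the eCRF, not a place in a table. A later SAP could settle the programming, but Section 11.1.1 is protocol text that sites follow.

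**Conclusion.** The classification rule is wrong as written: it is internally inconsistent with the endpoint, collection and recording sections. Applied literally, it gives no class to an unlisted, non-serious, non-IME event with onset on Days 0-7 in any group, or on Days 29-35 in Group C. Such an event would be recorded but could drop out of both the solicited and unsolicited summaries and out of the formal WHO causality classification.

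The size is 8 uncovered days in Groups A and B and 15 in Group C, at the nominal dose days. Under the literal rule, unlisted events in the week after dose 2 would count almost entirely in A and B and almost not at all in C, so the comparison by interval would be uneven. A reader might take 22.2%, 18.6% and 26.3% as shares of AEs missed. They are shares of calendar days; the documents give no event rates from which a share of events could be derived. The conclusion assumes that the Day 8-28 sentences are programmed as they stand.

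**What to change.** In Section 11.1.1, Section 10.1.5 and the synopsis, replace the Day 8-28 sentence with one definition. An unsolicited AE is:

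- (a) any AE not prelisted in the diary with onset on Days 0-28 after any dose; or
- (b) a prelisted term with onset on Days 8-28 after the most recent dose.

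Add that, where windows overlap, every event, listed or not, is attributed to the most recent dose for by-dose summaries. This also removes the double classification in Groups A and B. State that the WHO causality classification applies to all events under (a) and (b). The wording then agrees with Sections 3.2, 8.1, 8.3 and 11.6 and the schedule footnotes.

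The cost is one definition in three places and a matching eCRF and programming rule. It needs no extra visits, samples or subjects.
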